5.2 Treatment Regimen

1 mg/ml concentration of quinine in saline solution will be given to participants to instill in each. Doses will be administered by use of an LMA® MAD NASAL™ Intranasal Mucosal Atomization Device with 3mL syringe and vial adapter (Teleflex Medical, Research Triangle Park NC; item # MAD1400S), which is patient-specific, or other comparable device. If using a different device, the Sponsor will provide a statement confirming the devices' comparability or equivalence. Participants will do this twice per day for 4 weeks.

5.3 Method for Assigning Subjects to Treatment Groups

Urn Randomization²⁰ will be used to assign subjects to treatment groups. Urn randomization is a type of adaptive biased-coin randomization, where the probability of being assigned to the treatment arm changes as the balance of participants in the treatment and placebo groups changes. For example, when the first patient is added, assignment is based on simple randomization. If that patient is assigned to the treatment arm, then the probability of the 2nd patient being assigned to the treatment arm is decreased by a probability p . As patients are recruited, the probability of being assigned to either arm adapts in response to the size of each arm at the time of recruitment.

5.4 Preparation of Study Drug

IDS will prepare and record the distribution of the irrigant. The Clinical Research Coordinator or Clinical Research Nurse will pick up the solutions and will demonstrate the application to the subject. The application of the solution is exactly the same as if the study subject were to irrigate with regular saline as part of their daily regimen for chronic rhinosinusitis.

5.5 Subject Compliance Monitoring

In general, these are highly motivated patients who are seeking alternative therapy for traditional antibiotics. They have undergone surgical intervention (sometimes multiple surgeries). However, the measure of compliance will be determined by measuring the amount of solution remaining as the subjects return their irrigant bottles at the 4-week visit.

CONFIDENTIAL

5.6 Prior and Concomitant Therapy

The vast majority of our patients are typically using intranasal steroids. This is permitted during this trial. We will ask them not to use any conventional oral, or topically applied antibiotics. If the patient feels that their infection is progressing, we would ask that they return to the clinic for evaluation at which time, the treating physician can decide to place them on standard antibiotic therapy.

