1.5 Dose Rationale and Risk/Benefits

Our plan is to first study quinine against saline to determine efficacy and safety. The vast majority of patients with rhinosinusitis utilize low pressure / high volume (240mls) sinonasal lavage to cleanse the sinonasal cavity⁹. We propose to have the patients administer 6mls of quinine (1mg/ml) (same concentration that was used in the study mentioned above, which also activates NO production from human primary nasal cells *in vitro*) via a 3cc syringe with a mucosal atomizing device (MAD) on the tip. Patients will apply 3 mls to each nostril twice per day. Thus the patients will be exposed to a maximum of 12mls or 12.0 mg of quinine. In standard tonic water, quinine is 8.3mg/100mls and thus an 8oz glass of Canada Dry tonic water has 19.6mg of quinine. Thus, the maximum systemic exposure in our study (assuming ingestion of the total nasal administration) is less than drinking one glass of tonic water / day. To put this in context, the therapeutic range of quinine to treat malaria is 10mg/kg TID (2100mg for a 70kg individual) nearly 200 X the dose we are proposing.

We propose to enroll only patients who have had prior functional endoscopic sinus surgery (FESS) for two reasons: (1) better access to the sinonasal cavity to obtain microbiologic samples before, during and after the trial, and (2) patients with a marsupialized sinonasal cavity are not at risk for developing intra-orbital or intra-cranial complications from bacterial sinusitis, as a path of egress for the infection is widely patent into the nose.

2 Study Objectives

The overall objective of this study is to evaluate the efficacy of quinine nasal irrigations as a first line therapy for acute exacerbations of uncomplicated chronic rhinosinusitis following endoscopic sinus surgery.

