4.4 Early Withdrawal of Subjects

4.4.1 When and How to Withdraw Subjects

Subject may be withdrawn from the study prior to the expected completion of the protocol if the subject fails to adhere to protocol requirements, subject withdraws consent, or symptoms of acute rhinosinusitis exacerbation persist. Subjects will return to routine clinical care at that point.

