4.4.2 Data Collection and Follow-up for Withdrawn Subjects

Even though subjects may be prematurely withdrawn from the study, it is imperative to collect infection data (microbiology swabs) or symptomatic data. Such data is important to the integrity of the final study analysis since early withdrawal could be related to the tolerability profile or the ineffectiveness of the therapy. If a subject withdraws consent to participate in the study, attempts should be made to obtain permission to follow up with the subject's CRS for the duration of the 12-week follow-up period. Subjects with incomplete/missing data will not be included in the analysis.

5 Study Drug

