6.5 Statistical Methods

Data will be analyzed after 100 subjects have completed the study. Descriptive demographic data will be compiled including mean and median age, adjuvant therapy use, use of oral antibiotics, and microbiome profile. Longitudinal linear mixed effects modeling will be used to examine the relationship between all outcome measures and treatment assignment, assuming that the distribution of the outcome measures follow a unimodal symmetric distribution and satisfies the assumptions for mixed effects modeling. Mixed effects modeling takes advantage of all available data (up to the point of loss to follow-up or withdrawal) and also can address missing data. As long as the level of missingness is not excessive and patterns of missingness are not detected, mixed effects modeling can use all available data.²¹⁻²⁴ For all analyses, alpha will be set to 0.05 (two-sided).

The Epidemiology Department may be consulted at the completion of the study to assist with data analysis. Only de-identified data will be provided. No PHI will be shared.

CONFIDENTIAL

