6.6 Subject Population(s) for Analysis

All-randomized population: Any subject randomized into the study, regardless of whether they received study drug, will be analyzed.

7 Safety and Adverse Events

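### Section 4.4.2 excludes subjects with incomplete data, contrary to 6.5 and 6.6, and can drop treatment failures; separately, 5.6 requires no assessment at an unscheduled rescue visit

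*Combined protocol and SAP*

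**What the plan says.** **Withdrawal.** Section 4.4.1 says a subject may be withdrawn for non-adherence, for withdrawn consent, or if "symptoms of acute rhinosinusitis exacerbation persist. Subjects will return to routine clinical care at that point".

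**Data after withdrawal.** Section 4.4.2 says "it is imperative to collect infection data (microbiology swabs) or symptomatic data", on the ground that early withdrawal may reflect poor tolerability or an ineffective therapy. If consent is withdrawn, "attempts should be made to obtain permission to follow up" over the 12 weeks. The same paragraph then ends: "Subjects with incomplete/missing data will not be included in the analysis". It does not define incomplete.

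**Analysis.** Section 6.5: "Mixed effects modeling takes advantage of all available data (up to the point of loss to follow-up or withdrawal". Section 6.6: "Any subject randomized into the study, regardless of whether they received study drug, will be analyzed".

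**Rescue.** Section 5.6 asks a patient who feels the infection is progressing to come back for evaluation, when "the treating physician can decide to place them on standard antibiotic therapy". It names no SNOT-22, recorded endoscopy or culture to be obtained first. The Section 6 schedule has no unscheduled or early-termination visit; the first post-baseline assessment is at week 4 (+/- 7 days). Need for rescue antibiotics is itself a primary outcome (2.1, 3.2).

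**The concern.** Sections 4.4.2, 6.5 and 6.6 cannot all be followed. Under 4.4.2 the analysis is of completers; under 6.5 and 6.6 it is of all randomized subjects with whatever data they have. The choice would be left to whoever analyses the trial, after unblinding.

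The choice matters because the losses are not random. Persisting symptoms are a stated ground for withdrawal, so the subjects most likely to lack later visits are those in whom the irrigation failed. Section 4.4.2 recognises this and then excludes them. The objective in Section 2 is quinine as "first line therapy for acute exacerbations of uncomplicated chronic rhinosinusitis", and a comparison without the failures does not answer that question. If the exclusion covers the whole subject, it can also remove the rescue-antibiotic outcome that would have recorded the failure.

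A second, smaller gap lies in 5.6. A subject who progresses before week 4, is given antibiotics and is withdrawn may have no post-baseline value. Section 4.4.2 covers this only in part: it asks for swabs or symptoms rather than both, does not mention the endoscopy score, and sets no time relative to the antibiotic.

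**Working it through.** **The plan's own figure.** Section 6.4 gives 32 per group for a 95% CI half-width of 10 with SD 20. The half-width is c × 20 × √(2/n). With c = 1.96, n = 2 × (1.96 × 20/10)² = 30.7, so 31. With the t quantile, n = 32 (half-width 9.99; n = 31 gives 10.16). The stated 32 reproduces.

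**Precision at the planned size** (c = 1.96): 50 per arm gives 39.2 × √(2/50) = 7.8. Section 4.3 puts the first 10 enrolled on treatment without randomization. If they count toward the 100, which is not stated, about 45 per arm are randomized: 39.2 × √(2/45) = 8.3.

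**What each rule does with a subject**

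| Subject | 4.4.2 | 6.5 and 6.6 |
|---|---|---|
| Rescued, stays in, attends weeks 4 and 12 | included | included |
| Rescued and withdrawn after the week 4 visit | excluded if week 12 is missing | kept, with the week 4 value |
| Rescued and withdrawn before week 4, nothing further collected | excluded | kept, with baseline and the fact of rescue |

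The rules differ in the second and third rows. In the third row, deleting the exclusion restores the rescue outcome but adds almost nothing on SNOT-22, because no later value exists. That is the case for an assessment at the rescue visit.

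**Size if failures are dropped (illustration).** Taken from the documents: SD 20 (6.4). Assumed: a true difference of 10 (the 10 in 6.4 is a CI half-width, not an expected effect); placebo rescue r_p before week 4 of 10% to 30%; correlation ρ of 0.3 to 0.8 between clinical progression and SNOT-22; every rescued subject withdrawn and excluded.

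Model: progression is standard normal on placebo and shifted by 10/20 = 0.5 SD on quinine. Subjects below z = Φ⁻¹(r_p) are rescued, so quinine rescue is r_q = Φ(z − 0.5). With λ = φ/(1 − Φ), the observed difference is 10 − ρ × 20 × [λ(z) − λ(z − 0.5)].

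| r_p | r_q | λ(z) | λ(z − 0.5) | ρ | Observed difference |
|---|---|---|---|---|---|
| 0.10 | 0.037 | 0.195 | 0.085 | 0.3 | 9.3 |
| 0.20 | 0.090 | 0.350 | 0.178 | 0.5 | 8.3 |
| 0.30 | 0.153 | 0.497 | 0.279 | 0.8 | 6.5 |

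The shift is 0.7 to 3.5 points, below the half-width in every row.

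**Direction.** Excluding the worst fraction f of an arm moves its mean by ρ × 20 × φ(z_f)/(1 − f), where z_f = Φ⁻¹(f). The factor φ/(1 − f) is 0.195 at 10% and 0.350 at 20%, so a 10%/20% split shifts the difference by ρ × 20 × 0.155, or 0.9 to 2.5 points for ρ of 0.3 to 0.8. The larger loss on placebo understates the benefit by that amount; on quinine it overstates it by the same amount. Equal fractions give zero.

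**The case against.** **The statistical section would govern.** An analyst would probably follow 6.5 and 6.6, and the exclusion would never be applied. That is plausible, but no text sets the order, and 4.4.2 is an unqualified statement about the analysis.

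**Withdrawal is discretionary.** Section 4.4.1 says may, so not every rescued subject would be lost. This stands, and the figures, which drop all of them, lie toward the unfavourable end.

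**Much is already collected.** Section 3.1 makes cultures routine if pus is seen, Section 6 lists SNOT-22 and endoscopy as clinical care, and 4.4.2 presses for swabs or symptoms. This stands in part: Section 6 lists them for scheduled visits only, so the real addition is SNOT-22 and an endoscopy recording at an unscheduled visit.

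**Two stronger readings are tempting.** A reader might infer that lacking a pre-antibiotic assessment makes a rescued subject incomplete and so excluded. The documents do not support this. No such assessment is scheduled, so its absence leaves nothing incomplete; a rescued subject who attends weeks 4 and 12 is untouched by 4.4.2. A reader might also infer that values taken after rescue antibiotics are invalid. They are valid for a comparison of everyone as randomized, which fits 6.6, and rescue is counted as its own primary outcome. Wanting a no-rescue effect as well is a choice of estimand, not a correction. An analysis substituting pre-antibiotic values could err in either direction.

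**Conclusion.** The contradiction is an error as written and should be corrected. Applied literally, 4.4.2 can remove treatment failures, and the direction of the resulting bias depends on which arm fails more often. The size rests wholly on assumed rescue rates, correlation and effect. Under those assumptions a true difference of 10 would appear as about 9.3 to 6.5 with more failures on placebo. That is less than the sampling uncertainty, but it is systematic, and more patients would not reduce it. Only SNOT-22 was quantified, not Lund-Kennedy or culture.

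The gap in 5.6 is a separate and lesser matter. It affects subjects withdrawn at a progression visit before week 4, who may contribute baseline only, and closing it is an inexpensive improvement.

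**What to change.** 1. **Required.** Delete the last sentence of 4.4.2 so that 6.5 and 6.6 govern. This is a wording amendment with no other cost.
2. **Cheap improvement.** In 5.6 and Section 6, leave the rescue decision with the physician. Before the first antibiotic dose at an unscheduled progression visit, obtain SNOT-22 and a recording of any endoscopy done there for blinded scoring, with culture if pus is present as is already routine. Record the antibiotic start date, and follow rescued and withdrawn subjects to week 12 where they agree.

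The second change costs some coordinator time with patients already in clinic. Under the assumed rates the number of extra assessments runs from 45 × (0.10 + 0.037) = 6 to 50 × (0.30 + 0.153) = 23 over the whole trial.

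Keep the all-randomized comparison regardless of rescue as the main analysis. A sensitivity analysis using pre-antibiotic values is optional and not part of the required fix.

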5.7 Packaging

1 mg/ml concentration of quinine in saline solution will be given to participants to instill in each nostril. Product will be packaged in 90mL amber glass boston rounds, which have been autoclaved prior to use. A pharmaceutical press-in bottle adapter will be inserted into the neck and a child-resistant cap tightly placed onto the bottle. Doses will be administered by use of an LMA® MAD NASAL™ Intranasal Mucosal Atomization Device with 3mL syringe and vial adapter (Teleflex Medical, Research Triangle Park NC; item # MAD140OS), which is patient-specific. Participants will do this twice per day for 4 weeks. Subjects will clean the mucosal atomization device after each use with an alcohol swab.

Blinding of Study Drug

The placebo arm will be spiked with Sucrose Octaacetate which has a bitter taste, but does not stimulate sinonasal NO production.

5.8 Receiving, Storage, Dispensing and Return

5.8.1 Receipt of Drug Supplies

Upon receipt of the of the study supplies, an inventory must be performed and a receipt log filled out and signed by the person accepting the shipment. It is important that the designated study staff counts and verifies that the delivery from IDS contains the necessary items for the protocol.

5.8.2 Storage

Solutions can be stored at room temperature in the light protected bottles they are supplied with.

5.8.3 Dispensing of Study Drug

IDS will record and dispense the quinine or placebo.

5.8.4 Return or Destruction of Study Drug

At the completion of the study, there will be a final reconciliation of solution provided, consumed, and solution remaining. This reconciliation will be logged on the reconciliation form, signed and dated. Any discrepancies noted will be investigated, resolved, and documented prior to return or destruction of unused irrigant.

6 Study Procedures

	Clinical Care	Research
Baseline Visit (Week 0)	SNOT-22	Microbiome swab(s)
	CT Scan of Sinus (if clinically indicated)	Sniffin' Stick Test
	Nasal Endoscopy	Given Saline OR Quinine Solution
	Sinus culture swab(s)	Taste test
Irrigate Sinus 2 Times Every Day for 4 Weeks		
4 Week Visit (+/- 7 days)	SNOT-22	Microbiome swab(s)
	Sinus culture swab(s)	Sniffin' Stick Test
	Nasal Endoscopy	Return Unused Solution

CONFIDENTIAL

12 Week Visit (+/- 14 days)	SNOT-22	Microbiome swab(s)
	CT Scan of Sinus (if clinically indicated)	Sniffin' Stick Test
	Nasal Endoscopy	
	Sinus culture swab(s)	

6.1 Visit 1 (week 0)

Patients who consent to participate will be randomized to a treatment arm of quinine and saline (1mg/ml) or sucrose octaacetate (0.5mg/ml) in saline as dispensed by IDS. The study nurse coordinator will instruct the patient on how to administer the solution.

Following the routine endoscopically guided sinus culture swab, an additional research microbiome swab will be obtained. Patients will be asked to complete a routine Sinonasal Outcomes Test (SNOT-22) questionnaire as well as undergo a Sniffin' Stick Test as part of the research. Additionally, as part of their initial clinical assessment, a nasal endoscopy will be performed and recorded. This will later be scored by a blinded clinical investigator. If a CT scan of the sinuses is clinically indicated, then one will be performed. Additionally, a taste test to determine bitter taste sensitivity will be administered. This taste test is comprised of non-toxic solutions which are not swallowed by the patient.

6.2 Visit 2 (week 4, +/- 7 days)

Subject is asked to return to the clinic where they will be subjected to the same procedures at Visit 1. The clinical research nurse will measure and record the volume of nasal spray remaining in the stock bottle to determine compliance. No CT scan will be performed at the 2nd visit.

6.3 Visit 3 (week 12, +/- 14 days)

Subject is asked to return to the clinic where they will be subjected to the same procedures at Visit 1. A CT scan will only be performed if clinically indicated by the physician.

6.4 Sample Size Determination

There is no prior data to base a power calculation on. This trial will utilize a total of 100 patients to help guide future studies with appropriate power. In order to determine this sample size, we utilized a calculation that would ensure us that our confidence interval has a specified width. A previous study sampled over 300 CRS patients and found pre- and post-surgical SNOT-22 scores to have a standard deviation of about 20²¹. Based on this prior work, we estimate the required sample size to detect an effect with a precision of 10 (half the width of the desired 95% CI) to be 32 patients in each group. We will therefore recruit a total of n=100 patients in order to provide a margin for error, early withdrawal, or non-compliance.

6.5 Statistical Methods

Data will be analyzed after 100 subjects have completed the study. Descriptive demographic data will be compiled including mean and median age, adjuvant therapy use, use of oral antibiotics, and microbiome profile. Longitudinal linear mixed effects modeling will be used to examine the relationship between all outcome measures and treatment assignment, assuming that the distribution of the outcome measures follow a unimodal symmetric distribution and satisfies the assumptions for mixed effects modeling. Mixed effects modeling takes advantage of all available data (up to the point of loss to follow-up or withdrawal) and also can address missing data. As long as the level of missingness is not excessive and patterns of missingness are not detected, mixed effects modeling can use all available data.²¹⁻²⁴ For all analyses, alpha will be set to 0.05 (two-sided).

The Epidemiology Department may be consulted at the completion of the study to assist with data analysis. Only de-identified data will be provided. No PHI will be shared.

CONFIDENTIAL

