8.1	CONFIDENTIALITY.....	12
8.2	SOURCE DOCUMENTS	12
8.3	CASE REPORT FORMS.....	12
8.4	RECORDS RETENTION	12
9	STUDY MONITORING, AUDITING, AND INSPECTING	12
9.1	STUDY MONITORING PLAN.....	12
9.2	AUDITING AND INSPECTING	13
10	ETHICAL CONSIDERATIONS	13
11	STUDY FINANCES	13
11.1	FUNDING SOURCE.....	13
11.2	CONFLICT OF INTEREST	13
11.3	SUBJECT STIPENDS OR PAYMENTS	13
12	PUBLICATION PLAN	13
13	REFERENCES	14

CONFIDENTIAL

List of Abbreviations

CRS	Chronic Rhinosinusitis
NO	Nitric Oxide
FESS	Functional Endoscopic Sinus Surgery
HUP	Hospital of the University of Pennsylvania
CRF	Case Report Form
AE	Adverse Event
SAE	Serious Adverse Event
IDS	Investigational Drug Service

CONFIDENTIAL

Study Summary

Title	Efficacy and Safety of Adjuvant Topical Irrigation in the Treatment of Acute Exacerbation of Chronic Rhinosinusitis Following Functional Endoscopic Sinus Surgery (FESS)
Short Title	Topical Irrigation Therapy for CRS
Protocol Number	821731
Phase	II
Methodology	Randomized, double-blinded, placebo-controlled clinical trial.
Study Duration	3 years for accrual and follow up (+1 year for data analysis)
Study Center(s)	Single-center: Dept. of Otorhinolaryngology at HUP
Objectives	To evaluate the physiological differences between quinine-saline vs sucrose octaacetate-placebo nasal irrigations in subjects with CRS (both with and without polyps) as well as allergic fungal sinusitis.
Number of Subjects	Number of subjects projected for the entire study: 100
Diagnosis and Main Inclusion Criteria	Chronic Rhinosinusitis post FESS
Study Product, Dose, Route, Regimen	Nasal instillation of quinine sulfate and saline solution using a 3cc syringe adopted with an atomizer.
Duration of administration	Total duration of drug product administration (including any open-label lead-in, if applicable) is twice/day for 28 days.
Reference therapy	Desroisiers et al. (2001) findings showed that topical quinine in saline nasal solution was comparable, if not better to topical tobramycin (a commonly used antibiotic) for treatment of bacterial sinusitis.
Statistical Methodology	Longitudinal linear mixed-effects models to evaluate pre- and post-treatment continuous outcome scores.

CONFIDENTIAL

1 Introduction

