2.1 Primary Outcome Variable(s)

CONFIDENTIAL

The primary outcomes variables are:

- Pre- and post-treatment endoscopically guided sinonasal microbiologic cultures
- Pre- and post-treatment nasal endoscopy scored with the Lund-Kennedy scoring system by a blinded investigator¹⁸.
- Pre- and post-treatment quality of life questionnaires (22-item Sinonasal Outcomes Test [SNOT-22]).
- The necessity for rescue oral antibiotics for persistent infection.

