3.1 General Design

- This is a Randomized, double-blinded, placebo-controlled protocol
- The duration of subject participation is approximately 12 weeks
 - (Week 0) Screening/Baseline:
 - Microbiome swab obtained
 - Sniffin' Stick-12
 - Nasal Endoscopy (Lund-Kennedy Score)
 - CT scan (Lund-MacKay CT Score) if clinically indicated.
 - SNOT-22 survey
 - Nasal Irrigation distributed (Week 0)
 - 4 week period of nasal irrigation administration (2 times a day)
 - (Week 4)
 - Microbiome swab obtained
 - Nasal Endoscopy (Lund-Kennedy Score)
 - Sniffin' Stick-12 Microbiology/traditional swab*
 - SNOT-22 survey
 - (Week 12) Return to clinic for assessment of durable changes:
 - Microbiome swab obtained
 - Sniffin' Stick-12
 - Microbiology/traditional swab*
 - SNOT-22 survey
 - CT scan (Lund-MacKay CT Score) if clinically indicated

* Microbiology/traditional swabs are part of routine care if pus is evident during routine clinical nasal endoscopy.

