3.2 Primary Study Endpoints

- Efficacy of quinine and saline irrigations compared to saline irrigations alone.
- Changes in quality of life (SNOT-22 questionnaire) (both composite and subscale scores)
- Nasal endoscopy (Lund-Kennedy Score)
- Alterations in microbiology recovered (as determined by sinus microbiology culture)
- Whether or not conventional antibiotics were needed to treat the infection during or following the irrigation trial (as prescribed as part of routine care)

CONFIDENTIAL

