4.1 Inclusion Criteria

1. Patients diagnosed with chronic rhinosinusitis, with and without polyps, as well as allergic fungal sinusitis
2. Patients who have undergone Functional Endoscopic Sinus Surgery (FESS)
3. Purulent drainage on nasal endoscopy
4. Male or female subjects, 18 years of age or older
5. Patients seen at the Dept. of Otorhinolaryngology clinic at HUP, a tertiary care clinic.

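### The one planned model cannot fit the yes/no rescue-antibiotic primary; the culture primary has no scale or no-swab rule; the score analyses name no contrast or primary visit

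*Combined protocol and SAP*

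**What the plan says.** **Method.** Section 6.5 uses longitudinal linear mixed modelling to "examine the relationship between all outcome measures and treatment assignment, assuming that the distribution of the outcome measures follow a unimodal symmetric distribution". It names no other inferential method and does not say what happens if the condition fails. The Study Summary is narrower: "Longitudinal linear mixed-effects models to evaluate pre- and post-treatment continuous outcome scores".

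**Rescue antibiotics.** Section 2.1 lists as primary "The necessity for rescue oral antibiotics for persistent infection". Section 3.2 words it as "Whether or not conventional antibiotics were needed to treat the infection during or following the irrigation trial". That is one status per subject, with no pre-treatment value.

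**Culture.** Sections 2.1 and 3.2 make culture a primary outcome, described only as a change in what is recovered. No category, scale or success rule is given. The footnote in Section 3.1 says "Microbiology/traditional swabs are part of routine care if pus is evident during routine clinical nasal endoscopy". The visit table in Section 6 lists a culture swab at weeks 0, 4 and 12, and Sections 6.2 and 6.3 repeat the Visit 1 procedures at both follow-up visits. Section 4.1 requires "Purulent drainage on nasal endoscopy" at entry.

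**Incomplete data.** Section 4.4.2 leaves subjects with incomplete or missing data out of the analysis. Section 6.5 uses all data up to loss to follow-up or withdrawal, and Section 6.6 analyses everyone randomized.

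**Scores.** SNOT-22 and Lund-Kennedy are described as pre- and post-treatment (2.1), and SNOT-22 as changes (3.2). Irrigation ends at week 4, and Section 3.1 describes week 12 as a check on whether changes last. No section states a treatment-by-visit term or names a primary visit.

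**The concern.** Section 6.4 says the trial is meant to guide later, powered studies, so its effect estimates and intervals are its main product. For two of the four primary outcomes, a reader cannot tell from the plan what will be estimated. For the two scores, the visit and contrast can still be chosen after the data are seen. Section 6.5 adds to this by mentioning statistical help only as a possibility once the study is complete.

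Culture carries a further risk. Every subject has pus at entry. If follow-up swabs are taken only when pus is seen, a missing swab can mean that the subject improved. Whether that subject counts as a success, counts as a failure or is left out then affects the result, and the documents give conflicting rules on incomplete data.

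**Working it through.** **Inputs.** SD of SNOT-22 about 20, target 95% half-width 10, 32 per group, 100 in total (Section 6.4). The first 10 patients are not randomized (Section 4.3). Assumed: these 10 count toward the 100 and the rest split evenly and complete, so (100 - 10)/2 = 45 per arm. Event rates, no-pus rates and pre-post correlations are not in the documents and are shown as ranges.

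**1. The plan's own figure.** For a between-arm difference at one time point, n per group = 2(1.96 × 20/10)² = 30.7, so 31. With t quantiles the smallest n is 32 (half-width 9.99). The stated 32 is reproduced.

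**2. Rescue antibiotics against the condition in 6.5.** A 0/1 outcome with rate p has skewness (1 - 2p)/√(p(1 - p)): 2.67, 1.50, 0.87, 0.41 and 0 at p = 0.1, 0.2, 0.3, 0.4 and 0.5. It is symmetric only at p = 0.5, where it has two equal peaks. No rate gives both properties.

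For a risk difference with the same rate in both arms, the 95% half-width is 1.96√(2p(1 - p)/45): 12.4, 16.5, 18.9, 20.2 and 20.7 percentage points at the same five rates. With 45 per arm, an expected cell falls below 5 when total events, or total non-events, number fewer than 10 of 90. That is a pooled rate below 11.1% or above 88.9%.

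**3. Culture, if swabs depend on pus.** Let q be the no-pus rate in an arm and s the negative share among swabs taken.
- No swab counted as success: q + (1 - q)s
- No swab counted as failure: (1 - q)s

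Within an arm the two differ by q, so the estimated effect differs between codings by q₁ - q₀, whatever the values of s. Illustration with assumed q = 0.6 against 0.4 and s = 0.2 in both arms:

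| No swab counted as | Rates | Difference | 95% half-width |
|---|---|---|---|
| Success | 0.68 vs 0.52 | +16 points | 20 |
| Excluded (18 vs 27 swabbed) | 0.20 vs 0.20 | 0 | 24 |
| Failure | 0.08 vs 0.12 | -4 points | 12 |

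The zero in the middle row follows from setting s equal in both arms. The success-to-failure gap is 16 - (-4) = 20 points, equal to 60% - 40%. With q = 0.5 in both arms the gap is 0.

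**4. SNOT-22 contrast.** With SD 20 at each visit and pre-post correlation r, the SD is 20√(2(1 - r)) for change scores and 20√(1 - r²) after baseline adjustment. Half-width = t × SD × √(2/n):

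| | r = 0.3 | r = 0.5 | r = 0.7 |
|---|---|---|---|
| Change, 32 per arm | 11.8 | 10.0 | 7.7 |
| Adjusted, 32 per arm | 9.5 | 8.7 | 7.1 |
| Change, 45 per arm | 9.9 | 8.4 | 6.5 |
| Adjusted, 45 per arm | 8.0 | 7.3 | 6.0 |

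Only change scores at 32 per arm with r below 0.5 miss the target of 10. The documents give no SD for Lund-Kennedy, so no matching figures can be given for it.

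**The case against.** **A linear model on 0/1 data already estimates a risk difference.** This is correct, so it would be too strong to say that Section 6.5 offers no effect measure for rescue antibiotics. But the outcome fails the plan's own condition, no fallback is written, and under the Study Summary's scope it has no method. The reference list includes a paper on discrete longitudinal outcomes, but Section 6.5 cites it only in support of using all available data.

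**Baseline handling and visit are not blank.** This also stands in part. Pre/post modelling of change is indicated, and week 4 is the natural post-treatment visit because treatment ends there and week 12 is described as durability. What is missing is an explicit contrast and a formal choice of visit. Baseline as a covariate is a gain in precision, not the filling of a gap.

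**The footnote may only label swabs as routine care.** That reading is possible, because the Section 6 table lists swabs under clinical care. The conflict then needs one clarifying sentence. It matters only at follow-up: the entry criterion ensures pus at week 0, so the absence of a traditional swab from the week 0 list in Section 3.1 has no effect.

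**Week 12 endoscopy is implied.** Section 3.1 omits it from the week 12 list but includes a swab whose footnote presupposes endoscopy, and Sections 6 and 6.3 include it. This looks like an incomplete list and is minor.

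**Conclusion.** The point holds for three gaps. First, the stated method does not fit the rescue-antibiotic primary at any event rate; this rests on no assumption. Second, the culture primary has no scale and no rule for unswabbed subjects, and the text on follow-up swabs and on incomplete data conflicts. Third, the score analyses lack a stated treatment-by-visit contrast and primary visit.

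A reader might infer that improvers will be dropped and the culture result biased. The documents do not establish this. It requires the Section 3.1 footnote to override the visit table, Section 4.4.2 to override Sections 6.5 and 6.6, and no-pus rates to differ between arms. The 20-point shift shown is an illustration with assumed rates; each estimate in it is within its half-width of zero, and the shift is nil if no-pus rates are equal.

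A reader might also infer that the sample size is wrong. It is not: 32 per group is reproduced, and with 45 per arm every score option tabulated meets the 10-point target. Baseline adjustment narrows the SNOT-22 half-width from 9.9/8.4/6.5 to 8.0/7.3/6.0 at assumed correlations of 0.3/0.5/0.7.

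These gaps should be closed before unblinding.

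**What to change.** 1. Limit the linear mixed model to the continuous scores, and align Section 6.5 with the Study Summary.
2. Analyse rescue antibiotics as one binary outcome per subject through week 12. Report a risk difference with a 95% interval suited to small counts, and use Fisher's exact test if any expected cell, events or non-events, is below 5. State how withdrawn subjects count, since Section 4.4.1 allows withdrawal when symptoms persist.
3. Define a binary culture endpoint at a named visit. Reconcile Sections 3.1, 6, 6.2 and 6.3 on follow-up swabs, and Sections 4.4.2, 6.5 and 6.6 on incomplete data. State how a subject with no swab because no pus was seen is counted, with the other codings as sensitivity analyses. Analyse it as for rescue antibiotics, checking expected counts on the actual denominators.
4. For SNOT-22 and Lund-Kennedy, fit visit and treatment-by-visit terms with baseline as a covariate. Name the primary visit, for example week 4 as end of treatment with week 12 as durability. Reconcile the week 12 endoscopy entry in Section 3.1 with Sections 6 and 6.3.

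The cost is SAP wording, one endpoint definition and a few sensitivity analyses. Reconciling the schedules could add some procedures if swabs are to be taken at every visit.
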